4. INVESTIGATIONAL AGENT: EPACADOSTAT (INCB24360)

4.1 Preclinical Data

Epacadostat is a novel selective inhibitor of indoleamine 2,3-dioxygenase 1 (IDO1) manufactured by Incyte corporation. In cell-based assays, epacadostat potently inhibits IDO in both human tumor cells and human dendritic cells resulting in reduced tryptophan to kynurenin conversion (IC₅₀ values = 7.1-12.7 nM), and does not significantly inhibit other proteins that could impact

tryptophan catabolism.

To test whether epacadostat could reverse the inhibitory effect of IDO1 on T cells, IDO1+ DCs were cocultured with either CD4+ or CD8+ T cells in the presence of a soluble anti-CD3 antibody to promote T-cell activation and growth. Compared with the T cells cocultured with immature DCs, which do not express IDO1, 3H-thymidine incorporation in CD4+ or CD8+ T cells was significantly suppressed when they were cocultured with DCs, which express high levels of IDO1. Addition of epacadostat to the cocultures protected CD4+ or CD8+ T cells from this inhibitory effect. The effects of epacadostat in this system were dose-dependent and were consistent with the potency of the compound in blocking Trp conversion, with an EC50 value of 17.7 ± 4.7 nM (n = 3). In these same cultures, the effect of INCB24360 on cytokine levels was examined. Epacadostat treatment led to a 5-fold increase in the IFN- γ levels produced by CD4+ and CD8+ T cells when compared with vehicle control. Like T cells, NK cell proliferation was also inhibited by IDO1-mediated Trp catabolism, and epacadostat treatment reversed this, resulting in a 4- to 5-fold increase in 3H-thymidine uptake by NK cells.

Recent studies have also shown the potential for IDO1 activity to promote the differentiation of naïve T cells to cells with a regulatory T phenotype (Treg). The ability of IDO1+ DCs to promote differentiation to Treg cells as well as the ability of epacadostat to reverse this effect was therefore examined in an *in vitro* culture system similar to those previously reported. In these studies, co-culture of naïve CD4+CD25- T cells with IDO1+ DCs resulted in a 2-fold increase in Treg cells as defined by Foxp3 staining when the cells were cultured with interleukin (IL)-2. Inclusion of epacadostat in the cultures reversed this effect.

In Vitro Activity of Epacadostat on Human Immune Cells

Cell Type	Effects of IDO1	Epacadostat Effects
T cells	Decreased proliferation	Enhanced proliferation; enhanced IFN-
		gamma production
NK cells	Decreased proliferation	Enhanced proliferation
T _{reg}	Increased cell numbers	Decreased cell numbers
DC	Increased apoptosis	Decreased apoptosis; increased DC
		activation markers

4.2 Clinical Data to Date

As of October 2016, a 12 Incyte-sponsored clinical studies have been completed or are ongoing. Epacadostat was evaluated in a multi-center, dose-escalation Phase 1 study (INCB 24360-101) in subjects with refractory solid tumors using a 3 + 3 design to determine the safety and tolerability, PK, and pharmacodynamics of escalating oral doses of epacadostat. Epacadostat was well tolerated at doses up to 700 mg BID. Fatigue and nausea were the most frequently reported treatment-related treatment-emergent adverse event (48.1%, 25 subjects). Two DLTs occurred, including 1 DLT for radiation pneumonitis and 1 DLT for fatigue. An MTD was not determined..

There is an ongoing Phase I/II study of the safety, tolerability, and efficacy of pembrolizumab in

Version Date: 11/09/2017

combination with epacadostat in subjects with selected solid tumors, followed by an open-label expansion in subjects with select tumors (INCB 24360-202). This study enrolled 22 subjects with advanced melanoma on the Phase I portion of the study, of which 19 were treatment naïve. The overall response rate was 58% (11 of 19 patients), with 26% achieving a complete response and 32% achieving a partial response. 3 patients (16%) had stable disease and 14 patients (74%) achieved disease control.³² Responses were observed in all epacadostat dose cohorts greater than or equal to 50 mg BID and at all sites of target lesions. Responses were also observed in patients with previously treated advanced melanoma (1 complete response, 1 stable disease, n=3), nonsmall cell lung cancer (5 partial responses, 2 stable disease, n=12), renal cell carcinoma (3 partial responses, 5 stable disease, n=11), endometrial adenocarcinoma (1 complete response, 1 partial response, n=7), transitional cell carcinoma (3 partial responses, n=5), triple negative breast cancer (2 stable disease, n=3), and head and neck squamous cell carcinoma (1 partial response, 1 stable disease, n=2).³²

The safety profile for the 300mg BID dose of epacadostat in combination with pembrolizumab in the Phase I/II study (INCB24360-202) did not exceed the MTD in that study. While there was a higher incidence of grade 3 rash in the 300mg BID cohort compared to the 100mg BID cohort, these did not qualify as protocol-specified DLTs. The dose combination of 100mg BID of epacadostat plus pembrolizumab is currently being evaluated in a Phase III melanoma study (INCB24360-301). The epacadostat 100mg BID dose combination is being moved forward as the recommended dose in combination with pembrolizumab because of the lower incidence of dose interruptions and dose reductions compared to the 300mg BID dose.

4.3 Other Agent(s): Pembrolizumab

Pharmaceutical and Therapeutic Background

The importance of intact immune surveillance in controlling outgrowth of neoplastic transformation has been known for decades. Accumulating evidence shows a correlation between tumor-infiltrating lymphocytes (TILs) in cancer tissue and favorable prognosis in various malignancies. In particular, the presence of CD8+ T-cells and the ratio of CD8+ effector T-cells / FoxP3+ regulatory T-cells seems to correlate with improved prognosis and long-term survival in many solid tumors.

The PD-1 receptor-ligand interaction is a major pathway hijacked by tumors to suppress immune control. The normal function of PD-1, expressed on the cell surface of activated T-cells under healthy conditions, is to down-modulate unwanted or excessive immune responses, including autoimmune reactions. PD-1 (encoded by the gene Pdcd1) is an Ig superfamily member related to CD28 and CTLA-4 which has been shown to negatively regulate antigen receptor signaling upon engagement of its ligands (PD-L1 and/or PD-L2). The structure of murine PD-1 has been resolved. PD-1 and family members are type I transmembrane glycoproteins containing an Ig Variable-type (V-type) domain responsible for ligand binding and a cytoplasmic tail which is responsible for the binding of signaling molecules. The cytoplasmic tail of PD-1 contains 2 tyrosine-based signaling

Version Date: 11/09/2017

motifs, an immunoreceptor tyrosine-based inhibition motif (ITIM) and an immunoreceptor tyrosine-based switch motif (ITSM). Following T-cell stimulation, PD-1 recruits the tyrosine phosphatases SHP-1 and SHP-2 to the ITSM motif within its cytoplasmic tail, leading to the dephosphorylation of effector molecules such as CD3ζ, PKCθ and ZAP70 which are involved in the CD3 T-cell signaling cascade. The mechanism by which PD-1 down modulates T-cell responses is similar to, but distinct from that of CTLA-4 as both molecules regulate an overlapping set of signaling proteins. PD-1 was shown to be expressed on activated lymphocytes including peripheral CD4+ and CD8+ T-cells, B-cells, T regs and Natural Killer cells. Expression has also been shown during thymic development on CD4-CD8- (double negative) T-cells as well as subsets of macrophages and dendritic cells. The ligands for PD-1 (PD-L1 and PD-L2) are constitutively expressed or can be induced in a variety of cell types, including non-hematopoietic tissues as well as in various tumors. Both ligands are type I transmembrane receptors containing both IgV- and IgC-like domains in the extracellular region and contain short cytoplasmic regions with no known signaling motifs. Binding of either PD-1 ligand to PD-1 inhibits T-cell activation triggered through the T-cell receptor. PD-L1 is expressed at low levels on various non-hematopoietic tissues, most notably on vascular endothelium, whereas PD-L2 protein is only detectably expressed on antigenpresenting cells found in lymphoid tissue or chronic inflammatory environments. PD-L2 is thought to control immune T-cell activation in lymphoid organs, whereas PD-L1 serves to dampen unwarranted T-cell function in peripheral tissues. Although healthy organs express little (if any) PD-L1, a variety of cancers were demonstrated to express abundant levels of this T-cell inhibitor. PD-1 has been suggested to regulate tumor-specific T-cell expansion in subjects with melanoma (MEL). This suggests that the PD-1/PD-L1 pathway plays a critical role in tumor immune evasion and should be considered as an attractive target for therapeutic intervention.

Pembrolizumab is a potent and highly selective humanized monoclonal antibody (mAb) of the IgG4/kappa isotype designed to directly block the interaction between PD-1 and its ligands, PD-L1 and PD-L2. KeytrudaTM (pembrolizumab) has recently been approved in the United Stated for the treatment of patients with unresectable or metastatic melanoma, patients with metastatic NSCLC whose tumors have high PD-L1 expression [(Tumor Proportion Score (TPS) \geq 50%)] as determined by an FDA-approved test, with no EGFR or ALK genomic tumor aberrations, and no prior systemic chemotherapy treatment for metastatic NSCLC, patients with metastatic NSCLC whose tumors express PD-L1 (TPS \geq 1%) as determined by an FDA-approved test, with disease progression on or after platinum-containing chemotherapy. Patients with EGFR or ALK genomic tumor aberrations should have disease progression on FDA-approved therapy for these aberrations prior to receiving. Approval was also received for patients with recurrent or metastatic HNSCC with disease progression on or after platinum-containing chemotherapy.

Recently, pembrolizumab received accelerated approval for treatment of adult and pediatric patients with unresectable or metastatic, microsatellite instability-high (MSI-H) or mismatch repair deficient (dMMR) solid tumors that have progressed following prior treatment and who have no satisfactory alternative treatment options, as well as patients with MSI-H or dMMR colorectal cancer following progression on a fluoropyrimidine, oxaliplatin, and irinotecan.

Preclinical and Clinical Trial Data

Version Date: 11/09/2017

Refer to the Investigator's Brochure for Preclinical and Clinical data.

Rationale for Dose Selection/ Regimen/ Modification

An open-label Phase I trial (Protocol 001) is being conducted to evaluate the safety and clinical activity of single agent MK-3475. The dose escalation portion of this trial evaluated three dose levels, 1 mg/kg, 3 mg/kg, and 10 mg/kg, administered every 2 weeks (Q2W) in subjects with advanced solid tumors. All three dose levels were well tolerated and no dose-limiting toxicities were observed. This first in human study of MK-3475 showed evidence of target engagement and objective evidence of tumor size reduction at all dose levels (1 mg/kg, 3 mg/kg and 10 mg/kg Q2W). No MTD has been identified to date. Recent data from other clinical studies within the MK-3475 program has shown that a lower dose of MK-3475 and a less frequent schedule may be sufficient for target engagement and clinical activity.

PK data analysis of MK-3475 administered Q2W and Q3W showed slow systemic clearance, limited volume of distribution, and a long half-life (refer to IB). Pharmacodynamic data (IL-2 release assay) suggested that peripheral target engagement is durable (>21 days). This early PK and pharmacodynamic data provides scientific rationale for testing a Q2W and Q3W dosing schedule.

A population pharmacokinetic analysis has been performed using serum concentration time data from 476 patients. Within the resulting population PK model, clearance and volume parameters of MK-3475 were found to be dependent on body weight. The relationship between clearance and body weight, with an allometric exponent of 0.59, is within the range observed for other antibodies and would support both body weight normalized dosing or a fixed dose across all body weights. MK-3475 has been found to have a wide therapeutic range based on the melanoma indication. The differences in exposure for a 200 mg fixed dose regimen relative to a 2 mg/kg Q3W body weight based regimen are anticipated to remain well within the established exposure margins of 0.5 – 5.0 for MK-3475 in the melanoma indication. The exposure margins are based on the notion of similar efficacy and safety in melanoma at 10 mg/kg Q3W vs. the proposed dose regimen of 2 mg/kg Q3W (i.e. 5-fold higher dose and exposure). The population PK evaluation revealed that there was no significant impact of tumor burden on exposure. In addition, exposure was similar between the NSCLC and melanoma indications. Therefore, there are no anticipated changes in exposure between different indication settings.

The rationale for further exploration of 2 mg/kg and comparable doses of pembrolizumab in solid tumors is based on: 1) similar efficacy and safety of pembrolizumab when dosed at either 2 mg/kg or 10 mg/kg Q3W in melanoma patients, 2) the flat exposure-response relationships of pembrolizumab for both efficacy and safety in the dose ranges of 2 mg/kg Q3W to 10 mg/kg Q3W, 3) the lack of effect of tumor burden or indication on distribution behavior of pembrolizumab (as assessed by the population PK model) and 4) the assumption that the dynamics of pembrolizumab target engagement will not vary meaningfully with tumor type.

Version Date: 11/09/2017

The choice of the 200 mg Q3W as an appropriate dose for the switch to fixed dosing is based on simulations performed using the population PK model of pembrolizumab showing that the fixed dose of 200 mg every 3 weeks will provide exposures that 1) are optimally consistent with those obtained with the 2 mg/kg dose every 3 weeks, 2) will maintain individual patient exposures in the exposure range established in melanoma as associated with maximal efficacy response and 3) will maintain individual patients exposure in the exposure range established in melanoma that are well tolerated and safe.

A fixed dose regimen will simplify the dosing regimen to be more convenient for physicians and to reduce potential for dosing errors. A fixed dosing scheme will also reduce complexity in the logistical chain at treatment facilities and reduce wastage.

5. STUDY DESIGN

5.1 General study design

This is a single-arm Phase 2 study to evaluate the efficacy of combined epacadostat and pembrolizumab in advanced imatinib-refractory GIST patients.

Study Intervention: All subjects will receive pembrolizumab 200 mg IV every 3 weeks and epacadostat 100 mg PO BID continuously.

Schedule of Evaluations: Subjects will have regularly scheduled study visits at the clinical site on Day 1 of every cycle (CXD1), where safety assessments, including laboratory assessments, vital signs, and physical examinations will be performed (see Section 12 for detailed study evaluations, and Section 13 for study calendar).

Response to treatment will be determined by CT scans of the chest, abdomen, and pelvis with contrast. The overall response rate for the primary endpoint evaluation will be determined by RECIST v1.1 criteria; however, clinical decision making may be made based on immune related RECIST (irRECIST) criteria to allow treatment beyond initial progression (see section 15). In patients who are unable to get a CT scan w/ contrast due to renal function (or any other reason), an MRI with and without contrast may be used instead. Imaging will be performed at the following time points:

Baseline scan	Baseline scan within 4 weeks prior to first treatment
Weeks 1 – 24	Every 6 weeks +/- 1 week (at weeks 6, 12, 18, 24)
Weeks 25 – until disease	Every 12 weeks +/- 1 week (at weeks 36, 48, 60, 72, 84, 96, 108)
progression	
2 years	If subjects achieve ongoing disease control at 2 years, patients will be taken off study treatment and observed with imaging every 12 weeks +/- 2 weeks. If the patient develops disease progression, the option of reinitiating study therapy may be considered.

Version Date: 11/09/2017

Duration of treatment: Subjects will continue treatment until confirmed radiographic disease progression, intolerable toxicity or side effects (see Section 6.6 for Criteria for Withdrawal) or ongoing disease control at 2 years. In the latter case, imaging will be performed every 12 weeks, and should the patient develop evidence of disease progression, the option of reinitiating study therapy may be considered based upon discussion with the study principal investigator.

Biopsies for correlative studies: All enrolled subjects must undergo paired biopsies for correlative studies. CT-guided biopsies will be collected at baseline and between C2D1 and C3D1 of therapy for correlative studies. An optional biopsy for research purposes at the time of progression will also be discussed with these patients, however, is not mandatory. Subjects in whom biopsy is technically not feasible or in whom would result in unacceptable risk, in the opinion of the investigator, may be exempted from the biopsy requirement with discussion with the principal investigator.

Duration of follow-up: Adverse events and laboratory tests will be graded using the NCI CTCAE v4.0 scoring system. Adverse events will be assessed continuously during the study and for **90 days** after the last dose of treatment. Subjects will be followed for at least **90 days** post-study, or until all treatment related adverse events have recovered to baseline or are deemed irreversible by the investigator. Subjects who are removed from study for reasons other than progression of disease will be followed every 3 months with imaging to evaluate disease status and survival analysis while the study remains open.

5.2. Number of subjects

Using a Simon two-stage design, 12 patients will be treated initially. If an objective response is observed in at least 1 patient, we will proceed with enrollment of an additional 9 patients for a total of 21 evaluable patients. Assuming a 10% drop-out rate, we anticipate a total maximal accrual of 23 patients.

6. SUBJECTS SELECTION AND WITHDRAWAL

6.1. Inclusion Criteria

The following criteria are required for inclusion in the study:

- 1. Histologically confirmed diagnosis of GIST.
- 2. Unresectable or metastatic GIST.
- 3. Allowable prior therapies:

Version Date: 11/09/2017

- a. Subjects must have had clinical or radiographic progression on imatinib. Those who were taken off of imatinib for intolerance must have progressed on at least one other TKI.
- b. Subjects must have received ≥ 1 prior systemic therapy (including imatinib). A maximum of 4 prior therapies for metastatic disease are allowed.
- 4. Male or female subjects, age 18 years or older.
- 5. ECOG performance status ≤ 1 (Appendix A)
- 6. Life expectance of ≥ 3 months.
- 7. Laboratory parameters within the following Protocol-defined range. All screening laboratory tests should be performed within 28 days of treatment initiation and must be independent of hematopoietic growth factor support.
 - Absolute neutrophil count $\geq 1.5 \times 10^9/L$.
 - Platelets $\geq 100 \times 10^9/L$.
 - Hemoglobin ≥ 9 g/dL (transfusion is acceptable to meet this criteria)
 - Serum creatinine ≤ 1.5 x institutional upper limit of normal (ULN) OR calculated creatinine clearance ≥ 50 mL/min for subjects with creatinine levels ≥ 1.5 x institutional LH N
 - Aspartate aminotransferase, alanine aminotransferase, alkaline phosphatase $\leq 2.5 \text{ x}$ ULN, or $\leq 5 \text{ x}$ ULN in subjects with liver metastases.
 - Total bilirubin < 1.5 x ULN
 - Note: patients with hyperbilirubinemia clinically consistent with an inherited disorder of bilirubin metabolism (eg, Gilbert syndrome) will be eligible at the discretion of the principal investigator.
 - International normalized ratio (INR) or prothrombin time (PT) < 1.5x ULN unless subject is receiving anticoagulation therapy as long as PT or INR is within therapeutic range of intended use of anticoagulant.
 - Activated partial thromboplastin time (aPTT) < 1.5 x ULN unless subject is receiving anticoagulant therapy, as long as PTT is within therapeutic range of intended use of anticoagulants.
- 8. Presence of baseline measureable disease by RECIST v1.1 for solid tumors, defined as at least one lesion that can be accurately measured in at least one dimension (longest diameter to be recorded for non-nodal lesions and short axis for nodal lesions) as ≥ 20 mm with conventional techniques or as ≥ 10 mm with spiral CT scan, MRI, or calipers by clinical exam. (See Section 15.4 for the evaluation of measurable disease).
- 9. The effects of pembrolizumab and epacadostat on the developing human fetus are unknown, and thus female subjects of childbearing potential (defined as women who have not undergone surgical sterilization with a hysterectomy and/or bilateral oophorectomy, and are not postmenopausal (defined as ≥ 12 months of amenorrhea)) must have a negative pregnancy test at screening and must agree to use adequate contraception (complete

Version Date: 11/09/2017

abstinence, or two methods of birth control (Appendix B)) prior to study entry and until at least 4 months after the last dose of study treatment. Should a woman become pregnant or suspect she is pregnant while she or her partner is participating in this study, she should inform her treating physician immediately.

- 10. Fertile men must also agree to use adequate contraception (2 barrier methods or abstinence) during the study and for up to 4 months after the last dose of study drug.
- 11. All subjects must agree to pre- and on-treatment tumor biopsies. Subjects in whom biopsy is technically not feasible or in whom would result in unacceptable risk, in the opinion of the investigator, may be exempted from the biopsy requirement with discussion with the principal investigator. Use of outside archived tumor tissue for a baseline biopsy is not permitted.
- 12. Willingness and ability to provide written informed consent prior to any study-related procedures and to comply with all study requirements.

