15.2. Definitions

Evaluable for objective response: Only those patients who have measurable disease present at baseline, have received at least one cycle of therapy, and have had their disease re-evaluated will be considered evaluable for response. These patients will have their response classified according to the definitions stated below. (Note: Patients who exhibit objective disease progression prior to the end of cycle 1 will also be considered evaluable.)

Evaluable Non-Target Disease Response: Patients who have lesions present at baseline that are evaluable but do not meet the definitions of measurable disease, have received at least one cycle of therapy, and have had their disease re-evaluated will be considered evaluable for non-target disease. The response assessment is based on the presence, absence, or unequivocal progression of the lesions.

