15.3. Disease Parameters

Measurable disease: Measurable lesions are defined as those that can be accurately measured in at least one dimension (longest diameter to be recorded for non-nodal lesions and short axis for nodal lesions) as \geq 20 mm by chest x-ray, as \geq 10 mm with CT scan, or \geq 10 mm with calipers by clinical exam. All tumor measurements must be recorded in millimeters (or decimal fractions of centimeters).

Note: Tumor lesions that are situated in a previously irradiated area might or might not be considered measurable. If the investigator thinks it appropriate to include them, the conditions under which such lesions should be considered must be defined in the protocol.

Malignant lymph nodes: To be considered pathologically enlarged and measurable, a lymph node must be ≥ 15 mm in short axis when assessed by CT scan (CT scan slice thickness recommended to be no greater than 5 mm). At baseline and in follow-up, only the short axis will be measured and followed.

Version Date: 11/09/2017

Non-measurable disease: All other lesions (or sites of disease), including small lesions (longest diameter <10 mm or pathological lymph nodes with ≥ 10 to <15 mm short axis), are considered non-measurable disease. Bone lesions, leptomeningeal disease, ascites, pleural/pericardial effusions, lymphangitis cutis/pulmonitis, inflammatory breast disease, and abdominal masses (not followed by CT or MRI), are considered as non-measurable.

Note: Cystic lesions that meet the criteria for radiographically defined simple cysts should not be considered as malignant lesions (neither measurable nor non-measurable) since they are, by definition, simple cysts. Cystic lesions thought to represent cystic metastases can be considered as measurable lesions, if they meet the definition of measurability described above. However, if non-cystic lesions are present in the same patient, these are preferred for selection as target lesions.

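### Inclusion criterion 8 admits lymph nodes from 10 mm short axis, but Section 15.3 requires 15 mm on CT, so a patient with only a smaller node could be enrolled without being evaluable for objective response

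*Combined protocol and SAP*

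**What the plan says.** Criterion 8 in Section 6.1 starts from "Presence of baseline measureable disease by RECIST v1.1 for solid tumors, defined as at least one lesion". Its size limits for that lesion are "as ≥ 20 mm with conventional techniques or as ≥ 10 mm with spiral CT scan, MRI, or calipers by clinical exam". On the dimension to use, it specifies "longest diameter to be recorded for non-nodal lesions and short axis for nodal lesions". Nodes are thus expressly covered, with no threshold of their own. The criterion then refers the reader elsewhere: "See Section 15.4 for the evaluation of measurable disease".

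Section 15.3 opens with nearly the same general definition, including short axis for nodes. Its paragraph on malignant lymph nodes then says that, to be measurable, "a lymph node must be ≥ 15 mm in short axis when assessed by CT scan". Its paragraph on non-measurable disease includes "pathological lymph nodes with ≥ 10 to <15 mm short axis), are considered non-measurable disease".

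Section 15.2 limits evaluability for objective response: "Only those patients who have measurable disease present at baseline" qualify, subject to further conditions on treatment and re-assessment. It also defines a second class, evaluable for non-target disease response, for patients whose baseline lesions can be assessed but are not measurable.

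Section 17.3 keeps all eligible patients in the main response analysis, except possibly those who took no study drug. It treats categories 4 to 9, which include not assessable, as treatment failure. Section 17.1 plans 12 patients in stage 1 and 21 evaluable patients in all, with 23 enrolled.

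**The concern.** A node of 10 to under 15 mm short axis on CT satisfies the wording of criterion 8 and is non-measurable under Section 15.3. For most patients this does not matter, because another lesion will qualify. It matters when that node is the only lesion offered as measurable disease.

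Such a patient would pass eligibility but fall outside the Section 15.2 definition of evaluable for objective response. The plan does not then say clearly what happens. Section 15.2 suggests that the patient does not count towards the 21 evaluable patients. Section 17.3 suggests that the patient stays in the denominator, because he or she is eligible. In the first case a spare enrolment place is used. In the second the denominator contains a patient for whom a partial response cannot be measured, since that requires a target lesion. The trial succeeds on three responses among 21, with power barely above its 80% target, so a single patient is visible in the operating characteristics.

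**Working it through.** **Placing the rules side by side**

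| Place | Rule for a lymph node |
|---|---|
| 6.1, criterion 8 | 10 mm short axis by spiral CT, MRI or calipers; 20 mm by conventional techniques |
| 15.3, opening paragraph | General 10 mm rule for CT or calipers, short axis for nodes |
| 15.3, nodal paragraph | 15 mm short axis on CT |
| 15.3, non-measurable disease | 10 to under 15 mm short axis is non-measurable |
| 15.4 (the section that criterion 8 cites) | No CT threshold for nodes; palpable nodes are among the superficial lesions accepted from 10 mm by calipers |

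The 15 mm rule therefore sits in a section to which criterion 8 does not refer.

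**Reproducing the design**

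Inputs from Section 17.1: null rate 5%, target rate 20%, n1 = 12, stop at 0 responses, n = 21, success at 3 or more. Let X be the stage 1 responses and Y the stage 2 responses.

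Power = 1 − [P(X=0) + P(X=1)·P(Y≤1) + P(X=2)·P(Y=0)]

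At 20%, with X from 12 patients and Y from 9:
- P(X=0) = 0.8^12 = 0.0687; P(X=1) = 12·0.2·0.8^11 = 0.2062; P(X=2) = 66·0.04·0.8^10 = 0.2835
- P(Y=0) = 0.8^9 = 0.1342; P(Y≤1) = 0.1342 + 9·0.2·0.8^8 = 0.4362
- Power = 1 − (0.0687 + 0.0899 + 0.0380) = 0.803

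At 5%, the exact type I error is 0.080 and the chance of stopping after stage 1 is 0.95^12 = 0.540. These agree with the stated power of at least 80%, the 10% limit and the 54%.

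**One node-only patient who occupies a place and counts as a failure**

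*In stage 1* (11 patients can respond, then 9):
- P(X=0) = 0.8^11 = 0.0859; P(X=1) = 11·0.2·0.8^10 = 0.2362; P(X=2) = 55·0.04·0.8^9 = 0.2953
- Power = 1 − (0.0859 + 0.2362·0.4362 + 0.2953·0.1342) = 1 − 0.2286 = 0.771
- Early stopping under the null rises to 0.95^11 = 0.569; type I error falls to 0.071

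*In stage 2* (12 patients, then 8 who can respond):
- P(Y=0) = 0.8^8 = 0.1678; P(Y≤1) = 0.1678 + 8·0.2·0.8^7 = 0.5033
- Power = 1 − (0.0687 + 0.2062·0.5033 + 0.2835·0.1678) = 1 − 0.2200 = 0.780
- Type I error falls to 0.072

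Two such patients, one in each stage, would give 0.746. The number of such patients is an assumption throughout.

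**One node-only patient treated as non-evaluable**

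The plan enrols 23 for 21 evaluable, so 23 − 21 = 2 places are spare. If one is free, 21 evaluable patients are still reached and power stays at 0.803. If both have gone to ordinary dropout, 20 remain (12 + 8). The arithmetic is then that of the stage 2 case, 0.780.

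**The case against.** The strongest reply is that criterion 8 invokes RECIST v1.1, as the synopsis does without stating a threshold, and can be read as the general rule that the nodal paragraph of 15.3 supplements. The opening of 15.3 uses almost the same general wording before adding its nodal rule. Eligibility is also verified centrally from source reports before treatment (Sections 7.1 and 21.5). This makes an erroneous enrolment less likely, but does not remove the gap. The criterion writes out its own definition, names nodes in it, and cites 15.4 rather than 15.3. Central verification can only apply the definition that it is given.

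Three stronger readings are tempting, and the documents do not support them.

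- *Such a patient is certain not to respond.* Section 15.2 provides non-target evaluation, and the complete-response definition in 15.5.1 (written for irRECIST) lets a non-target node qualify by shrinking below 10 mm short axis. A measured partial response is ruled out; a complete response is not.
- *Such a patient always costs one of the 21 places.* Under Section 15.2 the patient is not one of the 21, and the enrolment allowance can absorb the loss.
- *The sample size is wrong.* The design figures reproduce.

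A shortcut for the power loss also misleads slightly. Diluting the rate to 20% × 20/21 = 19.05% for everyone gives 0.773, which is not the power with one fixed non-responder.

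**Conclusion.** The inconsistency is real and minor. Criterion 8 and Section 15.3 set different nodal thresholds, so a patient whose only lesion is a node of 10 to under 15 mm could be enrolled without being evaluable for objective response.

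The size depends on three assumptions: that such a patient occurs (no frequency is given, and it is assumed low), that he or she has no other measurable lesion, and how Sections 15.2 and 17.3 are reconciled. For one patient counted as a failure within the 21, power is 0.771 or 0.780 rather than 0.803. For one treated as non-evaluable, nothing is lost unless the two spare places are already used, in which case power is 0.780. The failure case sets aside the possible complete response through non-target assessment, so its figures show the full loss. Type I error falls in the failure case, so the risk is a missed signal and not a false positive.

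**What to change.** - In criterion 8, state that a lymph node counts as measurable only if it is at least 15 mm in short axis on CT or MRI, matching 15.3, and add 15.3 to the cross-reference. Section 15.3 names only CT, so extend its nodal sentence to MRI.
- Reconcile the opening paragraph of 15.3, and the caliper rule for palpable nodes in 15.4, with the same nodal threshold. Changing 6.1 alone would leave criterion 8 in conflict with the section that it cites.
- Update the eligibility checklist.

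The cost is a few phrases and a checklist line; the design stays at 12 and 21. The downside is that a rare patient with only a small node is no longer eligible.
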